29.0 Process to Document Consent in Writing

If your research presents no more than minimal risk of harm to subjects and involves no procedures for which written documentation of consent is normally

required outside of the research context, the IRB will generally waive the requirement to obtain written documentation of consent.

(If you will document consent in writing, attach a consent document. If you will obtain consent, but not document consent in writing, attach a consent script. Review "CHECKLIST: Waiver of Written Documentation of Consent (HRP-411)" to ensure that you have provided sufficient information. You may use "TEMPLATE CONSENT DOCUMENT (HRP-502)" to create the consent document or script.)

29.1 Describe whether you will be following "SOP: Written Documentation of Consent (HRP-091)." If not, describe whether and how consent of the subject will be obtained including whether or not it will be documented in writing.

Response: yes, following

30.0 Drugs or Devices

30.1 If the research involves drugs or device, describe your plans to store, handle, and administer those drugs or devices so that they will be used only on subjects and be used only by authorized investigators.

Response: n/a

If the drug is investigational (has an IND) or the device has an IDE or a claim of abbreviated IDE (non-significant risk device), include the following information:

30.2 Identify the holder of the IND/IDE/Abbreviated IDE.

Response: n/a

30.3 Explain procedures followed to comply with FDA sponsor requirements for the following:

FDA Regulation	Applicable to:		
	IND Studies	IDE studies	Abbreviated IDE studies
21 CFR 11	X	X	
21 CFR 54	X	X	
21 CFR 210	X		
21 CFR 211	X		
21 CFR 312	X		
21 CFR 812		X	X
21 CFR 820		X	

Response: n/a

Title: University at Buffalo Study of Nutrition and Activity in Kids (UB-SNAK)

Date updated: July 2, 2020

IRB approved: July 13, 2020

Hypotheses:

- 1) We hypothesized that sensitization to HED food is positively associated with zBMI gain over time
- 2) Sensitization to LED food is negatively associated with zBMI gain over time
- 3) Sensitization of HED and LED would interact with one another to impact zBMI change
- 4) The relationship between sensitization to HED food and zBMI gain is moderated by DD.

Sample Size Determination and Analytic Plan:

The sample size for this study was based on our prior studies in adults (Temple et al., 2014; Clark et al., 2010) that examined the relationship between sensitization, BMI, and weight change (effect size 0.19). We determined that, with an alpha of 0.05 and a power of 0.80, statistical significance could be achieved with a total of 180 participants.

In order to assess changes in zBMI over time and to account for missing values, we used multilevel modeling. To assess whether covariates are related to missingness, we examined baseline difference between those with complete versus incomplete data. There were no significant differences between these groups for child and parent BMI, race, sensitization, pubertal development, and food insecurity (all $p > 0.05$). We examined the scatterplots of zBMI data with each independent variable and observed that the data are linear.

To test our primary hypotheses related to zBMI change over time, appointments (level 1) were nested within individuals (level 2) and models included month of visit, sex, DEBQ score, pubertal development score and baseline zBMI as fixed effects. Our dependent measure was zBMI at baseline and 6, 15, and 24 months. We used number of months between visits as our marker of time (i.e. 6, 15, and 24). To test hypotheses related to sensitization, we categorized people as “sensitizers” (> 1) or “satiators” (≤ 1) depending on their change in RRV of food from baseline to post. This threshold was chosen to account for participants who increased responding from baseline to post, even by a small amount, while allowing participants who did not change responding or who decreased responding to be considered together as satiators. To test hypothesis 1, we included HED sensitization in the model and examined interactions with time. To test hypothesis 2, we included LED sensitization in the model and examined interactions with time. To test hypothesis 3, we included both HED and LED sensitization in the model, we interacted each one individually with time, and we interacted them with each other and with time. Finally, to test hypothesis 4, we added DD as a fixed effect and interacted it with HED sensitization and visit to examine moderation.

- 1) Temple, J. L. Factors that influence the reinforcing value of foods and beverages. *Physiol. Behav.* **136**, 97-103, doi:10.1016/j.physbeh.2014.04.037 (2014).
- 2) Clark, E. N., Dewey, A. M. & Temple, J. L. Effects of daily snack food intake on food reinforcement depend on body mass index and energy density. *Am. J. Clin. Nutr.* **91**, 300-308, doi:10.3945/ajcn.2009.28632 (2010).

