11.0 Data Management

11.1 Describe the data analysis plan, including any statistical procedures.

Response:

Response: The data will be analyzed using SPSS and SYSTAT software once collection is complete.

2 Way ANOVAS with

Inde: Sex and BMI as predictors

Dep: Food reinforcement

Cov: SES

Variables of interest include:

BMI% pre/post

Sex

SES

Food reinforcement pre/post

Other analyses:

Assigned snack food

Self efficacy scores for health eating

11.2 Provide a power analysis.

Response: 3 level Dependent, 2-2level Independents.

Able to detect effect size of 0.25, 0.5, 0.75, 1.00, or 1.25 at alpha 0.05

>90 0.826 0.999 1.000 1.000 1.000

N>90 used to see small/medium to large effects and also have an even number of participants to evenly split recruitment groups (N= 226, 113 male, 113 female)

11.3 Describe the steps that will be taken to secure the data (e.g., training, authorization of access, password protection, encryption, physical controls, certificates of confidentiality, and separation of identifiers and data) during storage, use, and transmission.

Response: The Principal Investigator, [name], will be responsible for ensuring data integrity and safety monitoring for human subjects who are involved in the research by training all staff to abide by appropriate protocols, including data security, password protection, and GRP/CITI training. The project coordinator will monitor these training steps.

All data that are collected by the investigators are stored in password protected databases or in locked filing cabinets, where the information is only associated with a numeric identifier and not a subject's personal information.

11.4 Describe any procedures that will be used for quality control of collected data.

Response: Quality control checks are used for all calculations and manual data inputs. At least two experimenters will check all values via double data entry. Data collected via survey monkey or redcap will be downloaded.

11.5 Describe how data and specimens will be handled study-wide:

Response: Data will be stored in a password protected database. The data will not contain any identifying information. No Information will be removed from the laboratory.

11.6 What information will be included in that data or associated with the specimens?

Response: ID number associated with height and weight data. No specimens collected.

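### Does the SAP's 180 participants for 80% power at an effect size of 0.19 contain a sample-size error?

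*SAP*

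**What the plan says.** The SAP, under Sample Size Determination and Analytic Plan, bases its size on earlier adult work that "examined the relationship between sensitization, BMI, and weight change (effect size 0.19"), and concludes that "with an alpha of 0.05 and a power of 0.80, statistical significance could be achieved with a total of 180 participants". No effect-size metric, sidedness, test, within-person correlation, covariate R-squared or dropout allowance is given.

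The analysis that follows is a multilevel model of zBMI at baseline, 6, 15 and 24 months: "In order to assess changes in zBMI over time and to account for missing values, we used multilevel modeling". On adjustment, "models included month of visit, sex, DEBQ score, pubertal development score and baseline zBMI as fixed effects". Sensitization is split in two at a change in food reinforcement of 1, "allowing participants who did not change responding or who decreased responding to be considered together as satiators". The first hypothesis is directional ("sensitization to HED food is positively associated with zBMI gain over time"), and its test is the interaction with time: "To test hypothesis 1, we included HED sensitization in the model and examined interactions with time".

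Protocol sections 3.1 and 23.1 plan 226 participants. Protocol section 11.2 has its own power table for an ANOVA layout, with effect sizes from 0.25 upward and the remark "N>90 used to see small/medium to large effects". The analysis listed in section 11.1 has food reinforcement, not zBMI change, as its dependent variable.

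**The concern.** A reader who checks 180 with the default formulas does not get 180. If 0.19 is a correlation or a two-group f, tested two-sided at 5%, the requirement is about 212 to 220, and 180 analysed participants leave a 27 to 28% chance of missing the effect instead of the 20% claimed.

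This is also the SAP's only power statement for its four hypotheses, and nothing in it refers to sensitization by time, the term that tests hypotheses 1 and 2. Section 11.2 does not help, because it addresses a different analysis. At stake is how a null interaction would be read: someone might credit it with 80% power when that figure belongs to another test.

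**Working it through.** **Inputs.** From the SAP: effect size 0.19, alpha 0.05, power 0.80, N = 180. From the protocol: 226 enrolled. Everything else below is an assumption, labelled as such. Normal quantiles are 1.960 (two-sided), 1.645 (one-sided) and 0.8416 (80% power).

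**Step 1: try to reproduce 180 with single-measurement, unadjusted, two-sided formulas.**

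- Correlation, Fisher z: N = ((1.960 + 0.8416)/atanh 0.19)² + 3, with atanh 0.19 = 0.1923, gives 215.2, so 216.
- Power at 180: Φ(0.1923·√177 − 1.960) = 0.725. Power at 226: 0.819.
- The remaining rows use the noncentral F with 1 df, except d, which uses the normal formula.

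| Reading of 0.19 | N for 80% | Power at 180 | Power at 226 |
|---|---|---|---|
| r, Fisher z | 216 | 0.725 | 0.819 |
| partial r | 212 | 0.733 | 0.826 |
| two-group f | 220 | 0.717 | 0.812 |
| two-group d | 870 | 0.25 | 0.30 |
| f², one predictor | 44 | above 0.99 | above 0.99 |

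None gives 180. The readings run from 44 to 870, and the SAP does not choose among them.

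**Step 2: try the other ordinary routes.**

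- *One-sided 5%.* Correlation: ((1.645 + 0.8416)/0.1923)² + 3 = 170.1, so 171; power at 180 is 0.820. Dividing by 0.95 for an assumed 5% loss gives exactly 180.
- *Covariate-adjusted, two-sided, four covariates.* For r, f² = 0.0361/(1 − R² − 0.0361). For f, f² = 0.0361/(1 − R²). With assumed R² of 0.15 and 0.19, r needs 179 and 171, and f needs 187 and 179.
- *Repeated-measures between-group F, two-sided, no covariates, f = 0.19.* The noncentrality is N·0.0361·m/(1 + (m − 1)ρ) for m visits and correlation ρ. Two groups, four visits, ρ = 0.75 gives 179. Three groups, three visits, ρ = 0.5 gives 181.

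Several standard calculations therefore land on or near 180. Each needs something the SAP leaves unsaid, but none is exotic.

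**Step 3: look at the nearest textbook analogue of the planned test.** For a two-group group-by-time F test at f = 0.19, the noncentrality is N·0.0361·m/(1 − ρ). With four visits this needs 77 at ρ = 0, 40 at 0.5, 21 at 0.75 and 10 at 0.9. Across two to four visits the range is 10 to 111. This does not prove the multilevel interaction is well powered, because it assumes 0.19 is an f for the interaction. It does show that the 212 to 220 figures cannot be carried over to that test as a shortfall. The actual requirement cannot be computed, since the slope difference, variance components, correlation and share of sensitizers are not given.

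**Step 4: compare 180 with 226.** 180/226 = 79.6%, and 180/0.80 = 225. This fits 180 completers after about 20% loss, although neither document says so.

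**The case for a change.** The strongest case for a change is that the 80% has no stated test attached. This holds whatever 0.19 means: the sample-size text contains no slope difference, correlation or group split, and section 11.2 covers another outcome. Under the default two-sided correlation or f reading, power at 180 is below 80%. An uneven split lowers it further: if 0.19 is an equal-split f (d = 0.38) and sensitizers are an assumed 30% of the sample, power is 0.64 at 180 and 0.74 at 226. If 0.19 is a two-group d, power at 180 is only about 0.25. A few sentences would settle which reading is right.

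The gap in reporting stands in full. The inference that the figure is wrong does not. Each unfavourable number depends on a reading the SAP does not state, just as each favourable one does, and all the unfavourable ones come from single-measurement comparisons, not from a four-occasion interaction model. For the same reason, replacing the 80% with 72 to 73% would put in another figure that does not belong to the planned test.

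**Conclusion.** No error in the 180 is demonstrated, and no change to the plan follows. Two-sided, unadjusted, single-measurement formulas do not return it (212 to 220 for r or f). One-sided, covariate-adjusted and repeated-measures calculations do come close, under assumptions the SAP omits. What is established is missing detail: the metric, sidedness and test behind 0.19, whether 180 means enrolled or analysed, and how it relates to 226.

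Supplying that detail would help a reader but would alter nothing that is done. If 0.19 is a correlation or equal-split f, the planned 226 gives 0.81 to 0.83 two-sided power when all are analysed, so no further enrolment is called for. The multilevel model also retains participants with partial follow-up. The SAP is written in the past tense and already reports its missing-data comparison, so a revised power sentence could not reshape the design. Whether a null sensitization-by-time result is informative is better judged from the confidence interval on that term than from a planning figure. The conclusion rests on not knowing the metric of 0.19; a source showing it to be a two-group d would change the assessment of power, but nothing in the documents points to that.

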Child and Parent Food availability and Scarcity Questionnaires (FIQ): The survey module and the associated Food Security Scale were developed by researchers at the National Center for Health Statistics and Centers for Disease Control and Prevention. It has been shown to identify food-insecure households and households with very low food security with reasonably high specificity and sensitivity and minimal bias. The surveys are phrased differently to address the separate perspectives of parent/guardian and child, with the child form being 5 item and the adult containing 24 items. The VFS will also be administered which has more questions related to the child experience.

Healthy Eating self-efficacy questionnaire (SEHE): Self-efficacy to make healthy food choices will be measured using a nine-item scale developed for use with American adolescents (French, Story, Neumark-Sztainer, Fulkerson, & Hannan, 2001). The self-efficacy scale was used to assess participants' self-confidence for making healthy food choices in social situations (e.g., with friends), in emotional situations (e.g., bored) and in normal situations (e.g., at family dinner). Responses are rated on a six-point scale ranging from "not at all sure" to "very sure."

Demographic: Parents will complete a demographic questionnaire providing information about household income, education, profession, and race/ethnicity for themselves and a secondary caregiver, if applicable. The parent will also be asked to self-report the current stature of the child's secondary care giver, as well as any other adult caregivers that the child lives with.

Tanner Stage Evaluation: Boys and girls will be given line drawings of the 5 stages of pubertal development and asked to circle the one that looks most like them. Girls will be given drawings of breast development and boys will be given drawings of genital and pubic hair development. Parents will independently be given the same

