Perceived Stress Scale (PSS-10): Previous research has shown a positive association between childhood cumulative stress and BMI as well as decreased self-regulatory behavior (Evans, 2003). The inclusion of the c will allow us to control for the influence of general stress on BMI outcomes (Terzian, Moore, & Nguyen, 2010). We will also examine it as a potential moderator in the relationship between impulsivity and adolescent BMI.

Adolescent Risk taking Questionnaire (ARA): This questionnaire has been designed to assess the frequency of risk taking by the study population. The adolescent version will be administered to ensure that the questions asked are age appropriate. Adolescents (12-16 yo) are asked 60 questions about the frequency of engaging in substance use, violence, and other risk taking behaviors over the past 12 months. This questionnaire has been updated to include some rewording and new questions from Youth Behavioral Risk surveillance Survey (from which it is based) 2019.

Dutch Eating Behavior Questionnaire (DEBQ): At the end of the sequence of visits, participants will complete an eating questionnaire that assesses knowledge about dieting practices and dietary restraint measurements.

Power of Food Scale (PFS): The Power of Food Scale (PFS) assesses the psychological impact of living in food-abundant environments. It measures appetite for, rather than consumption of, palatable foods, at three levels of food proximity

(food available, food present, and food tasted). It is comprised of 15 statements pertaining to the availability, presence, and taste of food. Examples of statements include: "If I see or smell a food I like, I get a powerful urge to have some." The aggregate PFS score suggests degree of vulnerability to the various aspects of an obesogenic food environment, one that is filled with readily available, high-kilojoule, highly palatable food.

Hunger, Thirst Rating Scale: Participants will be asked to rate their degree of thirst, hunger, liking of the study foods and desire to eat the study foods on a 100mm analog scale ranging from "not at all" to "extremely". This rating will be performed at three different time points during each RRV visit.

24-hour food and exercise recall: At each visit, the child (with the assistance of the parent) will recall his/her dietary intake and physical activity for the previous 24 hours and current day. Any participant who has not complied with the study protocol will be rescheduled.

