14.0 Risks to Subjects

14.1 List the reasonably foreseeable risks, discomforts, hazards, or inconveniences to the subjects related to the subjects' participation in the research. Include as may be useful for the IRB's consideration, a description of the probability, magnitude, duration, and reversibility of the risks. Consider physical, psychological, social, legal, and economic risks.

Response:

The level of risk encountered by the participants in this experiment is NO GREATER THAN MINIMAL. There are no invasive techniques being used or substances that are potentially harmful. There is a low probability of risks from completing some of our study instruments, including risk of disclosure of information outside the context of the research study. Sub-clinical disordered eating behavior, such as dieting and food restriction, is assessed on our instruments, such as the DEBQ and the EDE-Q. These instruments are not meant to be diagnostic in the manner in which they are being administered and are being used in the context of the research to understand how desire to regulate food intake and engage in various forms of dieting may interact with our study measures to influence weight change over time. These are commonly used measures in this population and are not known to cause physical, psychological, social, legal or economic harm. Food scarcity is being assessed using two instruments in this study (VFS and FIQ). It is critical that we gather information about the child's perceived food scarcity, as we have preliminary data showing that the child's perception is more strongly related to weight change than the parent's perception. The child may feel some embarrassment from answering questions about their food scarcity, but all other risks (physical, social, legal, and economic) remain extremely low probability.

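### The H1–H4 models omit perceived stress, which the protocol collects to control for on BMI outcomes, and two other Visit 1 factors, so the sensitization-by-time effects may be confounded

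*SAP*

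**What the plan says.** The SAP, under Sample Size Determination and Analytic Plan, gives the covariates of the zBMI models: "models included month of visit, sex, DEBQ score, pubertal development score and baseline zBMI as fixed effects". H1 and H2 add HED or LED sensitization and its interaction with time. H3 adds both, with their interaction. For H4, "we added DD as a fixed effect and interacted it with HED sensitization and visit to examine moderation". No model contains stress, food scarcity or SES, and no reason is given. Food insecurity appears only in the comparison of children with complete and incomplete data.

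The protocol treats the three factors differently:

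- **Stress.** Protocol 9.2 says that including the Perceived Stress Scale (PSS) "will allow us to control for the influence of general stress on BMI outcomes". It adds: "We will also examine it as a potential moderator in the relationship between impulsivity and adolescent BMI".
- **Child-reported food scarcity.** Protocol 14.1 cites preliminary data that the child's "perception is more strongly related to weight change than the" parent's. It does not mention adjustment.
- **SES.** Protocol 11.1 names SES as the covariate of a two-way ANOVA with "Dep: Food reinforcement" and with sex and BMI as predictors. For the components, Protocol 9.2 says: "Parents will complete a demographic questionnaire providing information about household income, education, profession, and race/ethnicity".

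The measures timeline in Protocol 9.2 places the PSS, the child food insecurity form (FIQ-C) and the demographic form at Visit 1. The RRV tasks for HED and LED food begin at Visit 2.

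**The concern.** The sensitizer or satiator label is an observed trait, so each of H1 to H4 is an observational contrast. A factor related to both the label and the rate of zBMI change would create a sensitization-by-time effect where none exists, or mask a real one. As the models stand, a positive H1 could not be separated from a difference in stress, food scarcity or socioeconomic position, because no planned model examines those alternatives.

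The existing covariates do not settle this. Baseline zBMI is listed as a fixed effect with no product with month. It adjusts the level of zBMI, while the hypotheses concern the slope. The complete-versus-incomplete comparison addresses dropout and not confounding.

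Stress is the clearest omission. The protocol gives control of BMI outcomes as a reason for collecting it, zBMI is such an outcome, and the SAP drops it without comment. It also bears on H4: the protocol defines delay discounting as its measure of impulsivity and plans stress as a possible moderator of impulsivity and BMI, yet the H4 model has no stress term.

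**Working it through.** **1. Timing.** Protocol 9.2 timeline:

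| Measure | First visit |
|---|---|
| PSS | 1 |
| FIQ-C | 1 |
| Demographic form (SES components) | 1 |
| RRV HED/LED (source of the label) | 2 |

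Visit 1 values precede the exposure, so adjusting for them does not adjust for a consequence of sensitization.

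**2. The plan's own figure.** The documents give no figure for confounding. The only yardstick is the SAP's effect size of 0.19 with N = 180 (alpha 0.05, power 0.80), whose metric and sidedness are not stated. Read as a correlation, N = ((z_alpha + z_beta)/atanh(0.19))² + 3:

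- two-sided: ((1.960 + 0.842)/0.1923)² + 3, rounded up to 216
- one-sided: ((1.645 + 0.842)/0.1923)² + 3, rounded up to 171

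Neither gives 180. Shares of 0.19 quoted below are therefore indicative only, and nothing in the conclusion depends on them.

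**3. Size of a possible bias.** The documents give no correlation of any factor with the label or with the zBMI slope, so the values here are assumed. Each child's slope is treated as one number (single-level approximation). With no true effect,

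spurious r = r(label, factor) × r(factor, slope),

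and the two-sided rejection rate is 1 − Φ(1.96 − atanh(r)·√(n−3)) + Φ(−1.96 − atanh(r)·√(n−3)).

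Worked case, 0.2 × 0.2 = 0.04 at n = 226: atanh(0.04)·√223 = 0.598, so the rate is 1 − Φ(1.362) + Φ(−2.558) = 0.087 + 0.005 = 0.092.

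| One omitted factor: label, slope | Spurious r | n = 180 | n = 226 |
|---|---|---|---|
| 0.1, 0.1 | 0.01 | 5.2% | 5.3% |
| 0.2, 0.2 | 0.04 | 8.3% | 9.2% |
| 0.2, 0.3 | 0.06 | 12.6% | 14.6% |

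If 0.19 is a correlation, 0.04 to 0.06 is 21% to 32% of it. If the factor is unrelated to the label, the bias is zero.

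With three factors, much depends on how they relate to each other. At 0.15 and 0.15 each:

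- mutually independent: 3 × 0.0225 = 0.0675, about 17% at n = 226
- mutual correlation 0.3: 0.0675/1.6 = 0.042, about 10%

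**4. Cost of adjusting.** For a partial correlation of 0.19 with six existing predictors (assumed, single-level), adding three covariates changes power from 0.7330 to 0.7330 at N = 180 and from 0.8255 to 0.8255 at N = 226. Five covariates give 0.7329 and 0.8254. This holds the partial correlation fixed. If the covariates are correlated with the label, the variance of its coefficient is multiplied by 1/(1 − m·r²) for m independent factors: 1.04 for one factor at 0.2, and 1.14 for three.

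**The case against.** A reader might infer that the protocol promised to adjust the zBMI models for SES and for food scarcity, and that the SAP breaks both promises. The documents do not support this. SES is a covariate only where food reinforcement is the outcome and BMI is a predictor. The food scarcity statement is in the risk section, where it justifies asking the child at all. Only stress has an announced use for BMI outcomes, and even there the protocol names no model.

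A reader might also infer that H1 to H4 are in fact confounded. That needs one factor linked to both the label and the slope, and no passage links any factor to both. SES is tied to food reinforcement. Stress and scarcity are tied to BMI or weight. The label is a change in reinforcement, and a covariate for its level need not predict its change.

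It is fair, too, that the hypotheses are worded as associations and that the protocol speaks of prediction. For that aim the covariate set is partly a matter of choice, and an adjusted analysis beside the current one is enough for SES and scarcity. Finally, products of a covariate with month do not remove confounding of the H3 and H4 higher-order interactions.

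All of this stands. It narrows the point to possible confounding and one unreconciled variable. It does not explain why pre-exposure measures already scheduled for collection, one of them intended as a control, are in no model.

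**Conclusion.** The point holds in this limited form. The H1–H4 models compare unrandomised groups without perceived stress, contrary to its stated purpose, and without child-reported food scarcity or SES, which are sensible adjustment variables that the protocol did not commit to for zBMI. The sensitization-by-time effects may be confounded by factors measured before the exposure. Whether they are cannot be determined from the documents.

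The size rests wholly on assumed correlations and a single-level approximation. For one factor it runs from negligible, at 0.1 or below, to a type I error of about 8–15% in place of 5%, at 0.2 with the label and 0.2–0.3 with the slope. The plan can run as written, but a positive H1 would lack an inexpensive safeguard, so the change should be made.

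**What to change.** - Add the Visit 1 PSS score to the H1–H4 models, as a main effect and multiplied by month, in line with Protocol 9.2. If stress is to stay out, give the reason.
- Pre-specify an adjusted analysis that also adds Visit 1 FIQ-C and an SES measure, each with its product with month, and report it beside the current models. Define the SES measure from the demographic form (income, education or profession), since no composite is given.
- Use Visit 1 values only, because later ones may follow from the exposure.
- State that for H3 and H4 these terms adjust the slope but do not fully remove confounding of the higher-order interactions.
- The SAP is written in the past tense and reports a completed missingness check, so record whether the zBMI models had already been run when the terms were added.

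The cost is SAP wording and about six fixed-effect parameters (three factors × two terms, more if SES is categorical). Some SES answers will be missing, and precision falls modestly if the factors are correlated with the label. No new data are needed.
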